8.1.2 DEFINITION OF SERIOUS ADVERSE EVENTS (SAE)

An AE or suspected adverse reaction is considered "serious" if, in the view of either the Investigator or Sponsor, it results in any of the following outcomes:

- Death
- A life-threatening adverse event
- Inpatient hospitalization or prolongation of existing hospitalization
- A persistent or significant incapacity or substantial disruption of the ability to conduct normal life functions
- A congenital anomaly/birth defect

Important medical events that may not result in death, be life-threatening, or require hospitalization may be considered serious when, based upon appropriate medical judgment, they may jeopardize the patient or subject and may require medical or surgical intervention to prevent one of the outcomes listed in this definition.

8.1.3 DEFINITION OF UNANTICIPATED ADVERSE DEVICE EFFECT (UADE)

Unanticipated adverse device effect is any serious adverse effect on health or safety, any life-threatening problem or death caused by, or associated with a device, if that effect, problem, or death was not previously identified in nature, severity, or degree of incidence in the application, or any other unanticipated serious problem associated with a device that relates to the rights, safety, or welfare of subjects.

8.2 CLASSIFICATION OF AN ADVERSE EVENT

8.2.1 SEVERITY OF EVENT

The Investigator will be asked to assess the severity of the AE using the following categories:

- Mild:** Events require minimal or no treatment and do not interfere with the participant's daily activities.
- Moderate:** Events result in a low level of inconvenience or concern with the therapeutic measures. Moderate events may cause some interference with functioning.
- Severe:** Events interrupt a participant's usual daily activity and may require systemic drug therapy or other treatment. Severe events are usually potentially life-threatening or incapacitating.

8.2.2 RELATIONSHIP TO STUDY DEVICE AND/OR PROCEDURE

For all collected AEs, the clinician who examines and evaluates the participant will determine the AE's causality based on temporal relationship and his/her clinical judgment. The degree of certainty about causality will be graded using the categories below.

- Definitely:** The relationship of the AE and the study device or the study procedure can definitely be established.

- Probably:** While a clear relationship to the study device or to the study procedure cannot be established, the AE is associated with an expected AE or there is no other medical condition or intervention, which could explain the occurrence of such an event.
- Possibly:** There is no clear relationship between the AE and the study device or study procedure; however, one cannot definitely conclude that there is no relationship.
- Unrelated:** There is no relationship between the AE and the study device or study procedure. This may include but is not limited to the incident being an expected outcome of a previously existing or concurrent disease, concomitant medication or procedure the subject experienced.

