2.2 POTENTIAL RISKS AND BENEFITS

2.2.1 RISKS

Risks involved with this treatment are similar to risks of other standard treatments of wounds of this nature. Possible complications include infection, chronic inflammation (inflammation other than that which may occur immediately following application of product), allergic reaction, excessive redness, pain, swelling, or blistering. If any of these conditions occur, the dressing should be removed.

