8.3 TIME PERIOD AND FREQUENCY FOR EVENT ASSESSMENT AND FOLLOW-UP

The occurrence of an AE or SAE may come to the attention of study personnel during study visits or upon review by a study monitor. All AEs (per Investigator discretion) that are possibly impactful to the development or healing of the target wound will be captured on the appropriate CRF. Information to be collected includes event description, date of onset, clinician's assessment of severity, relationship to study products (assessed only by those with the training and authority to make a diagnosis), and time of resolution/stabilization of the event. All AEs will be followed to adequate resolution.

Any medical condition that is present at the time that the participant is screened will be considered as baseline and not reported as an AE. However, if the study participant's condition deteriorates at any time during the study, it will be recorded as an AE.

Changes in the severity of an AE will be documented to allow an assessment of the duration of the event at each level of severity to be performed. AEs characterized as intermittent require documentation of onset and duration of each episode.

The PI will record all reportable events with start dates occurring any time following initial device application through the last day of study participation. At each study visit, the Investigator will inquire about the occurrence of AE/SAEs since the last visit. Events will be followed for outcome information until resolution or stabilization.

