10.1.1 SAFETY ANALYSES

Safety will be assessed by wound examination, clinical laboratory tests and collection of AEs as outlined in the Schedule of Events. All summaries of AEs will be based on treatment-emergent AEs and presented using the incidence and a tabulation of the number of events. The number and percentage of subjects experiencing AEs will be summarized by system organ class and description. Summaries by maximum severity and relationship to the study treatment will also be provided. SAEs and AEs leading to discontinuation from the study will be presented by system organ class and preferred term.

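### The causality scale lets expectedness support a grade of Probably and pools device with procedure, so the relationship summary may misclassify common wound events and cannot reliably separate product-related from procedure-related AEs

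*Combined protocol and SAP*

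**What the plan says.** Section 8.2.2 has the examining clinician grade each AE on four levels, "based on temporal relationship and his/her clinical judgment". The levels pair the device with the procedure throughout:

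- *Definitely*: "The relationship of the AE and the study device or the study procedure can definitely be established".
- *Probably*: no clear relationship can be established, but "the AE is associated with an expected AE or there is no other medical condition or intervention" that could explain the event.
- *Possibly*: "There is no clear relationship between the AE and the study device or study procedure", yet a link cannot be ruled out.
- *Unrelated*: no relationship. "This may include but is not limited to the incident being an expected outcome of a previously existing or concurrent disease"; concomitant medication and a procedure the subject underwent are further examples.

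Section 8.2.3 treats expectedness as its own item, judged against the risk information for the products. Section 2.2.1 supplies that information: "Possible complications include infection, chronic inflammation (inflammation other than that which may occur immediately following application of product), allergic reaction", then redness, pain, swelling and blistering. It describes these risks as similar to those of other standard wound treatments.

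Two other sections describe the same assessment differently. Section 8.3 lists, among the items collected for each event, "relationship to study products (assessed only by those with the training and authority to make a diagnosis"). Section 10.1.1 states: "Summaries by maximum severity and relationship to the study treatment will also be provided".

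**The concern.** A causality scale should keep two questions apart: is this kind of event already known for the product, and did the product bring it about in this patient? The wording of *Probably* lets the answer to the first stand in for the answer to the second. Here that is weak evidence, because the listed risks are by the protocol's own account common to other wound treatments.

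The second difficulty is what the grade refers to. One field covers device and procedure in 8.2.2, products in 8.3 and treatment in 10.1.1, and nothing reconciles the three. The study adds biopsies of its own, so procedure-related events are a real possibility.

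At stake is how the relationship summary can be read. Section 4.1 describes a single-site observational study and no group treated with standard care alone. Clinician attribution is thus the main planned means of telling product events from background wound events.

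**Working it through.** The plan gives no figure that depends on the scale and no AE rates, so there is nothing to recompute. The check sets the definitions side by side and runs two events through them.

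| Grade (8.2.2) | Link to device or procedure | Further condition |
|---|---|---|
| Definitely | Established | None |
| Probably | Not clearly established | Expected-AE arm, **or** no alternative explanation |
| Possibly | None clear | Cannot be excluded |
| Unrelated | None | Examples: outcome of disease, medication or a procedure |

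**Event A: infection of a diabetic foot ulcer after an application, with the underlying disease a plausible cause.**

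1. Infection is listed in 2.2.1. If its nature, severity and frequency also fit the risk information, 8.2.3 does not make it unexpected.
2. *Probably*: the second arm fails because another condition could explain the event. The first arm is met, and the *or* makes it enough.
3. *Possibly*: also met if the clinician sees no clear link but cannot exclude one.
4. *Unrelated*: met instead of *Possibly* if the clinician attributes the infection to the disease, which is the stated example.
5. Whichever of *Possibly* and *Unrelated* the clinician's view supports, *Probably* is open as well. The grades are not mutually exclusive, and the expected-AE arm creates the overlap with *Unrelated*.

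**Event B: bleeding after the Visit 1 biopsy that needs additional treatment.**

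1. Section 8.1.1 keeps known sequelae of wound procedures out of AE recording unless extra treatment is needed or the course departs from what is expected. This event needs extra treatment, so it is recorded, provided it is judged possibly to affect the target wound (8.3).
2. Under 8.2.2 it is *Definitely* related if the biopsy is a study procedure. That term is not defined.
3. It could also be read as *Unrelated*, through the example of a procedure the subject underwent.
4. If the field means what 8.3 says (products), *Unrelated* is the natural grade.
5. Section 10.1.1 would tabulate it as related to study treatment, or not, according to which section the clinician followed. No second grade separates the possibilities.

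**Opportunity for such events.** Section 7.2.3 schedules 3 biopsies for normally healing wounds and 4 for delayed ones. The first precedes product application, and 8.3 records events that start after the initial application. A patient who completes the schedule therefore has 3 − 1 = 2 or 4 − 1 = 3 biopsies after AE recording has begun. This counts procedures; it is not a rate of misclassified AEs.

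**The case against.** The strongest reply is that the grade is a clinical judgement informed by timing, and the categories only express how certain the clinician is. A sensible clinician would grade a disease-driven infection *Unrelated*. Section 8.1.1 removes routine procedural pain and bleeding. Section 8.3 points to products, so the field may already be product-specific. Event descriptions are collected and summarised, so an event described as biopsy bleeding could still be picked out.

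Much of this stands, and it rules out several stronger readings that a reader might infer:

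- *That every AE of an expected type must be graded Probably.* The wording permits that grade and does not force it. Section 8.2.3 also looks at severity and frequency, so appearing in 2.2.1 does not alone make an event expected.
- *That debridement events will count as treatment-related.* Study procedure is undefined, sections 4.1 and 7.1 place debridement within standard of care and wound management, and *Unrelated* could cover it. The documents leave the matter open.
- *That UADEs cannot be identified.* Sections 8.1.3 and 8.4.3 define and report UADEs individually. Nothing derives them from this grade.
- *That better wording would show which events the product caused.* With no control group, no scale can prove causation.

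The reply does not remove the defect. Definitions exist to make judgement consistent, and these allow two answers for one event on the same clinical view. If the field is meant to be product-specific, the only scale defined for it still pools procedure with device. Event descriptions help with an obvious biopsy bleed, but less with infection or pain that could come from product, biopsy or disease.

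**Conclusion.** The point holds as a defect of definition and consistency. The *Probably* grade mixes expectedness with causality and overlaps *Unrelated*. Device and procedure share one grade, and 8.2.2, 8.3 and 10.1.1 name three different objects for it. The planned relationship summary may therefore misclassify common wound events and cannot reliably separate product-related from procedure-related AEs.

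Its reach is limited to descriptive safety reporting. The primary endpoints and sample size do not use the grade. The AE endpoints in 4.1.2 and 4.1.3 count wound-related or wound-specific events without reference to it. How many events would be misgraded cannot be derived from the documents.

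The conclusion assumes that clinicians apply the written definitions and that no CRF instruction outside these documents already splits the grade. It is worth acting on because the change is cheap and a pooled grade may not be separable once collected.

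**What to change.** 1. In 8.2.2, remove the expected-AE arm from *Probably* and require that no other condition or intervention is a more likely explanation. Requiring that nothing else could explain the event would be too strict: patients with chronic wounds nearly always have another possible cause, and the category could be left almost empty. Keep expectedness in 8.2.3 only.
2. Record two grades per AE: relation to Cytal/MicroMatrix, and relation to study procedure.
3. Define study procedure to include the protocol biopsies, and state whether standard-of-care debridement counts. Make clear that the procedure example under *Unrelated* does not refer to a study procedure.
4. Use the same terms in 8.2.2, 8.3 and 10.1.1.
5. In 10.1.1, tabulate the two grades separately. If grades are collapsed into related and unrelated, state which count as related.

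The cost is one extra CRF field per AE, one extra table and the wording changes, with slightly more data entry. The change should be made before AEs are collected on the pooled grade.

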8.2.3 EXPECTEDNESS

The Investigator will be responsible for determining whether an AE is expected or unexpected. An AE will be considered unexpected if the nature, severity, or frequency of the event is not consistent with the risk information previously described for the study products.

8.3 TIME PERIOD AND FREQUENCY FOR EVENT ASSESSMENT AND FOLLOW-UP

The occurrence of an AE or SAE may come to the attention of study personnel during study visits or upon review by a study monitor. All AEs (per Investigator discretion) that are possibly impactful to the development or healing of the target wound will be captured on the appropriate CRF. Information to be collected includes event description, date of onset, clinician's assessment of severity, relationship to study products (assessed only by those with the training and authority to make a diagnosis), and time of resolution/stabilization of the event. All AEs will be followed to adequate resolution.

Any medical condition that is present at the time that the participant is screened will be considered as baseline and not reported as an AE. However, if the study participant's condition deteriorates at any time during the study, it will be recorded as an AE.

Changes in the severity of an AE will be documented to allow an assessment of the duration of the event at each level of severity to be performed. AEs characterized as intermittent require documentation of onset and duration of each episode.

The PI will record all reportable events with start dates occurring any time following initial device application through the last day of study participation. At each study visit, the Investigator will inquire about the occurrence of AE/SAEs since the last visit. Events will be followed for outcome information until resolution or stabilization.

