7.2.2 TREATMENT VISIT (STUDY DAY #0)

1. Ensure subject remains eligible prior to study device application.
2. Document laboratory results and ABI (as required) for lower extremity wounds. Required labs include Hgb A1C (for diabetic subjects), pre-albumin and albumin.
3. Confirm negative pregnancy test for females of reproductive potential prior to initial device application.
4. Document and update changes to concomitant medication log and medical history.
5. Record AEs as reported by participant or observed by Investigator.
6. Perform wound SOC and application of product(s).
7. Document updates and/or changes to Employment and/or Ambulatory status.
8. Wound biopsy prior to product application for pathological evaluation.
9. Full wound evaluation and wound management as appropriate.
10. Wound photos to include one zoomed in photo before debridement, at least one zoomed in photo after debridement and at least one zoomed in photo after product application(if applied). All photos taken in accordance with standardized wound care photography protocols.

7.2.3 REGULAR STUDY VISITS #1-12 AS INDICATED (VISITS ARE SEQUENTIAL AND CONTIGUOUS, BASED OFF OF TREATMENT VISIT)

For All Follow-Up Visits:

1. Full wound evaluation and wound management as appropriate.
 - a. Wound photos to include one zoomed in photo before debridement, at least one zoomed in photo after debridement and at least one zoomed in photo after product application(if applied). All photos taken in accordance with standardized wound care photography protocols.

2. Study device application (up to a maximum of 10 applications between Weekly Follow-up Visit 1 - 12, unscheduled visits and the Initial Device Application at the Treatment Visit) as needed.
3. Assessment of target wound related Adverse Events.
4. Document and update changes to concomitant medication log and medical history
5. Document updates and/or changes to Employment and/or Ambulatory status.
6. Perform delayed wound healing labs & procedures (PRN, as determined by the Investigator).
7. Perform closure and recurrence assessment.

For Follow-Up Visit 6 & 12 ONLY (Wound SOC, FUV activities above, PLUS the following):

1. Document updates and/or changes to Employment and/or Ambulatory status.
2. Document laboratory results and ABI (as required) for lower extremity wounds. Required labs include Hgb A1C (for diabetic subjects), pre-albumin and albumin.
3. Quality of Life Assessments (Katz ADL, W-QoL, VAS).

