7.2.5 LONG-TERM FOLLOW UP VISIT & FINAL STUDY VISIT

(LTFU AT 26 WEEKS [182 DAYS] AND FSV AT 52 WEEKS [365 DAYS] FROM TREATMENT VISIT, ± 14 DAYS)

The following activities are required for the Long-Term Follow-Up Study Visit and the Final Study Visit:

1. Record any changes to employment and ambulatory status.
2. Document and update changes to concomitant medication log and medical history.
3. Record AEs as reported by participant or observed by Investigator.
4. Quality of Life Assessments (Katz ADL, W-QoL, VAS).
5. Perform a physical examination and wound SOC.
6. Perform delayed wound healing labs & procedures (PRN, as determined by the Investigator).
7. Collect updates to tobacco use.
8. Document laboratory results and ABI (as required) for lower extremity wounds (PRN at these visits, not required).
9. Perform closure and recurrence assessment.
10. Full wound evaluation and wound management.
 - a. Wound photos to include one zoomed in photo before debridement, at least one zoomed in photo after debridement (if performed). All photos taken in accordance with standardized wound care photography protocols.

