8. ASSESSMENT OF SAFETY

8.1 SPECIFICATION OF SAFETY PARAMETERS

8.1.1 DEFINITION OF ADVERSE EVENTS (AE)

Target wound related Adverse Events (AEs) will be captured from the time of initial treatment. An AE is defined as follows:

- Any adverse change in the subject's medical status when compared with the subject's baseline condition, whether or not the event is related to the device or a procedure; or
- An exacerbation (either in frequency or severity) in a subject's pre-existing condition.

Known sequelae, judged by the Investigator to be associated with target wound procedures (e.g., pain or bleeding associated with debridement) and/or the course of normal wound healing (e.g., slough or mild exudate) should not be recorded as an AE unless: 1) an additional treatment/procedure is required (e.g., use of a concomitant medication); or 2) the frequency, severity and/or duration deviates from the expected course. These include but are not limited to:

- Infection/sepsis
- Worsening of wound bed/failure to heal
- Increased chronic inflammation
- Allergic reaction
- Unexplained fever or chills
- Death
- Neurologic symptoms such as light headedness, headache
- Gastrointestinal symptoms including nausea and vomiting
- Pain

In some cases, an increase in wound size may be documented as an AE. This determination will be made using the following thresholds for overall change in wound size (**from baseline post-debridement measurement**):

- 0-25% - Does not require AE reporting
- 25-50% - Physician discretion – potential opportunity for further investigation of size changes.
- 50%+ - Must be reported as an AE.

The AE will be noted as “resolved” upon $\geq 10\%$ reduction (from largest wound size) maintained for 2 consecutive weeks.

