16. APPENDIX I: SCHEDULE OF EVENTS

Evaluation	Screening *	Treatment Visit	WEEKLY FOLLOW-UP VISITS												Week 26 (± 14 days) LTFU Visit	Week 52 (± 14 days) Final Study Visit	Unscheduled
			Week 1 (Visit 1)	Week 2 (Visit 2)	Week 3 (Visit 3)	Week 4 (Visit 4)	Week 5 (Visit 5)	Week 6 (Visit 6)	Week 7 (Visit 7)	Week 8 (Visit 8)	Week 9 (Visit 9)	Week 10 (Visit 10)	Week 11 (Visit 11)	Week 12 (Visit 12)			
Informed Consent	X																
Eligibility Assessment ¹	X	X															
Significant Medical, Surgical, Medication History	X																
Laboratory results & ABI (for lower extremity wounds) ²		X							X					X			X
Pregnancy test ³	X	X															
Employment & Ambulatory Status	X	X	X	X	X	X	X	X	X	X	X	X	X	X	X	X	X
Demographics, Social Info	X														X	X	
Physical Examination	X														X	X	X
Surveys (W-QoL, VAS, Katz)	X								X					X	X	X	
Independent 3 rd party wound assessment ⁴		X				X				X				X			
Wound photographs & planimetry ⁵	X	X	X	X	X	X	X	X	X	X	X	X	X	X			X
Delayed wound healing labs & procedures ⁶																	
Wound SOC activities	X	X	X	X	X	X	X	X	X	X	X	X	X	X	X	X	X
Wound evaluation ⁷	X	X	X	X	X	X	X	X	X	X	X	X	X	X			X
Wound management	X	X	X	X	X	X	X	X	X	X	X	X	X	X			X
Closure & Recurrence assessment			X	X	X	X	X	X	X	X	X	X	X	X	X	X	X
Cyral®/MicroMatrix® Applications ⁸		X	X	X	X	X	X	X	X	X	X	X	X	X			X
Study Wound related Adverse Events		X	X	X	X	X	X	X	X	X	X	X	X	X	X	X	X
Review Concomitant medications and Medical History		X	X	X	X	X	X	X	X	X	X	X	X	X	X	X	X
Biopsy and quantitative histopathology ⁹		X	X														

*--Screening Visit must occur within 7 days of Treatment Visit. The Screening Visit may be combined with the Treatment Visit, as long as all eligibility criteria have been confirmed prior to treatment.

1 – If Screening and Treatment Visits are not combined, verify that subject remains eligible prior to study device application (no need to repeat activities).

2 – ABI is PRN, as determined by the Investigator.

3 – Confirm a negative pregnancy test prior to study device application (test does not need to be repeated twice).

4 – Independent 3rd party expert will complete wound assessment as photographs are available. Additional assessments to be completed as appropriate.

5 – This is done through the use of the Silhouette Star camera system by Aranz®. To be completed at LTFU/FSV if applicable.

6 – PRN activity at all visits.

7 – Wound evaluations to be completed at LTFU/FSV if applicable.

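### The protocol gives two scopes for adverse events, wound-related only and unrestricted, so possibly device-related events outside the wound (mainly non-serious) can be absent from the safety tables

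*Combined protocol and SAP*

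**What the plan says.** Four places restrict collection to the wound:

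- Section 8.3: "All AEs (per Investigator discretion) that are possibly impactful to the development or healing of the target wound will be captured".
- Section 8.1.1, opening sentence: "Target wound related Adverse Events (AEs) will be captured from the time of initial treatment".
- Section 7.2.3, the list for Visits 1-12: "Assessment of target wound related Adverse Events".
- Appendix I, Schedule of Events, the only AE row, marked from the Treatment Visit through Week 52 and for unscheduled visits: "Study Wound related Adverse Events".

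Other places do not:

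- The definition in 8.1.1 covers any adverse change in medical status, "whether or not the event is related to the device or a procedure".
- Sections 7.2.2 (Treatment Visit), 7.2.4 (unscheduled) and 7.2.5 (Weeks 26 and 52) each say "Record AEs as reported by participant or observed by Investigator".
- Section 8.4.1 has AEs entered on the form as the investigator learns of them, with no wound condition.
- Section 8.3 itself adds that a deterioration in the participant's condition is recorded as an AE.

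Section 8.2.2 grades causality for AEs that have been collected. Section 10.1.1 bases safety on AEs collected according to the Schedule and then promises: "The number and percentage of subjects experiencing AEs will be summarized by system organ class and description". It adds summaries by severity and by relationship to treatment, and tables of SAEs and of AEs leading to discontinuation.

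**The concern.** The restrictive rule asks whether the event may affect the wound. The safety question for a device is whether the device may have caused the event. These select different events. A transient systemic reaction to a porcine-derived product could bear on device safety and have no bearing on healing.

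The order of steps matters. If an event is screened out at collection, nobody grades its relationship to the device, and no later analysis can recover it. The tables in 10.1.1 are laid out like general safety tables, by system organ class and relationship, and nothing in that section says they are confined to wound-related events. A reader would take a low count of related events outside the skin as evidence about the device, when it may partly reflect the collection rule and one site's judgement of what might affect healing.

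**Working it through.** No stated figure is at issue, so the check applies each rule to one event: a non-serious systemic symptom soon after an application, possibly device-related, judged by the investigator to have no effect on the wound.

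| Place | Recorded? |
|---|---|
| 8.3, capture rule | No |
| 8.1.1, opening sentence | No, unless called wound-related |
| 8.1.1, definition | It is an AE |
| 7.2.3, Visits 1-12 | No |
| 7.2.2, 7.2.4, 7.2.5 (Treatment, unscheduled, Weeks 26 and 52) | Yes |
| Schedule of Events, all visits | No |
| 8.4.1 | Yes |

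Three things follow.

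1. **The answer depends on the section and the visit.** For the Treatment, unscheduled, Week 26 and Week 52 visits, Section 7.2 and the Schedule contradict each other. For Visits 1-12 they agree on the narrow scope.
2. **The narrow wording covers most of the exposure period.** The Schedule's footnote on applications allows 10 in total: one at the Treatment Visit and up to nine over Visits 1-12 and unscheduled visits. Weeks 26 and 52, after the application period, have the broad wording in 7.2.5.
3. **The filter reaches the tables.** Schedule row (wound-only), then causality grading of what was collected (8.2.2), then tables built on that collection (10.1.1). No section makes possible relation to the device a reason for capture in its own right.

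The symptom list in 8.1.1 does not settle the matter. It names allergic reaction, fever or chills, and neurologic and gastrointestinal symptoms, but it follows a sentence on when known sequelae should not be recorded. It is unclear whether the list gives events to record or events to leave out.

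**Illustration of sensitivity.** The documents give neither an event rate nor a capture fraction, so both are assumed here. Let p be the true rate of device-related events outside the wound, c the fraction captured, and n the number treated.

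- Chance of recording at least one event: 1 − (1 − pc)^n, taking p = 3% and n = 80.
- Upper two-sided 95% limit on the true rate when none is recorded: [1 − 0.025^(1/n)]/c. At c = 1 this is 4.5% for n = 80 and 3.6% for n = 100.

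| c | Chance of at least one recorded (p = 3%, n = 80) | Upper limit if 0 of 80 | Upper limit if 0 of 100 |
|---|---|---|---|
| 1 | 91% | 4.5% | 3.6% |
| 0.75 | 84% | 6.0% | 4.8% |
| 0.5 | 70% | 9.0% | 7.2% |
| 0.25 | 45% | 18.0% | 14.5% |

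The table shows how much the meaning of a zero count depends on c. It does not estimate c.

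**The case against.** **Wound-only collection is a declared choice.** Secondary objective 4 and secondary endpoint 4 concern wound-related AEs, the products are 510(k)-cleared, and the study is observational and not under an IDE. This stands as a justification for a wound-related endpoint. It does not explain why the definition, four visit types and 8.4.1 say otherwise, or why the tables in 10.1.1 carry no scope label.

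**Serious events are covered.** A reader might infer that serious device effects would go unreported. The documents do not support that. Sections 8.4.2 and 8.4.3 require notification of SAEs and UADEs without a wound condition, and the UADE definition reaches "any life-threatening problem or death caused by, or associated with a device". Section 10.1.1 also promises an SAE table. So the gap lies mainly in non-serious events. What remains is that the special routes describe notification, and the plan does not say that an event reported only that way is entered in the AE tables.

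**The filter is loose.** A possible effect on the wound is a low bar. Most risks named in 2.2.1 are local, and that section has the dressing removed if any of them occurs, allergic reaction included, which plausibly meets the bar. This stands and will reduce the loss. It still leaves the decision to investigator discretion and does not reach a systemic symptom judged irrelevant to healing.

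**Broader text protects capture.** It may in practice: 8.3 has the investigator ask about AEs at each visit, and 8.4.1 sends all AEs to the sponsor's quality group. But this text conflicts with the wound-only text, and the plan gives no rule for which prevails.

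**Conclusion.** The contradiction in AE scope is real and should be resolved before the safety tables are produced. With the restrictive sections followed as written, possibly device-related events without effect on the wound, mainly non-serious ones, can be missing from the tables by system organ class and relationship, and capture can differ between visits.

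A reader might go further and infer that such events will be missing, or that the tables understate device-related events by a known amount, for example 0 of 80 reported where 4 of 80 occurred (5% of 80 = 4). The documents do not support this. That 5% is invented, and the contrast assumes that every such event is lost despite the unrestricted visit lists and 8.4.1. A reader might also take all of Section 7.2 as unrestricted, but 7.2.3 is not.

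The size of the effect is not computable from the documents. No primary endpoint, sample size or efficacy result is touched. The conclusion rests on two readings: that the Schedule governs collection, as 10.1.1 says, and that an event with no bearing on the wound is not wound-related.

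**What to change.** Use one scope at every visit. Reconcile 7.2.2 to 7.2.5, 8.1.1, 8.3, 8.4.1, 10.1.1 and the Schedule row so that the case report form records:

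- every AE that may affect the target wound;
- every AE judged at least possibly related to the device or procedure, whatever its effect on the wound;
- all SAEs, UADEs and deaths.

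In 8.1.1, state whether the symptom list gives events to record or sequelae to leave out. In 10.1.1, tabulate all recorded events, say that those notified through the SAE and UADE routes are included, and put the scope in the table titles. Keep the wound-related AE endpoint as a separate subset table. If the sponsor prefers wound-only collection, the least that is needed is to make every section say so and to title the tables accordingly.

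The cost is protocol wording, a few more AE forms and possibly a slightly higher reported AE incidence. Sample size and the primary analysis do not change.
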